2. STUDY SCHEDULE AND TIMELINE

IBSOS is a prospective, randomized, multi-site clinical trial comparing three types of psychotherapy delivered in an individual format for severely affected adults with IBS. After a four-week baseline data collection period, participants will be randomly assigned to receive either four-session self-administered CBT, 10-session therapist-administered CBT or a control condition emphasizing support and education (allocation 1:1:1). The acute treatment phase will last 10 weeks. Participants will undergo follow-up examinations two weeks after treatment ends (week 12) and three, six, nine, and 12 months after the end of treatment.

IBSOS requires the expeditious enrollment of a sufficient number of participants to ensure the statistical power and generalization of study results. This trial plans to recruit 480 participants over an approximately four-year treatment delivery period. Assuming a relatively conservative pre randomization dropout rate of 25%, each site will need to phone telephone screen approximately 150 participants per year and enroll (consent) 75 in order to meet yearly recruitment quotas of 60 randomized participants at each site.

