2.1 Duration of Study and Visit Schedule

After a one-year clinical trial planning phase, the study will begin recruitment of 480 Rome diagnosed adults. Recruitment is scheduled to occur over 48 months. The acute treatment phase will be administered over 10 weeks. Participants assigned to standard CBT will attend 10 weekly sessions. Participants assigned to either the limited contact or attention control treatments will attend four clinic visits scheduled over 10 weeks. Participants will undergo post-treatment evaluation two weeks after their assigned treatment ends (week 12) and at quarterly intervals (three, six, nine, 12 months) out to 12 months. Follow-up of all participants will continue until the last participant randomized has completed 12 months of follow-up.

See Appendix 1: IBSOS Protocol Overview

See Appendix 2: IBSOS Detailed Work Flow

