3.4 Secondary Efficacy Endpoints

Secondary efficacy endpoints include the following:

- Adequate relief of abdominal pain two weeks after the end of treatment phase and at quarterly intervals through 12 months
- Adequate relief of bowel problems two weeks after the end of treatment phase and at quarterly intervals through 12 months
- Change from pre-treatment baseline of lower GI function (i.e. stool frequency; stool consistency; severity of urgency, bloating and straining) to post-treatment, and at quarterly follow-ups
- Change from pre-treatment baseline in ratings of (a) severity of abdominal pain/discomfort and (b) global severity of IBS symptoms to post treatment and at quarterly follow-ups
- Change from pre-treatment baseline in indices of health related quality of life to post treatment, and at quarterly follow-ups
- The percent of participants who describe themselves as satisfied with assigned treatment at 2-week follow-up using the Client Satisfaction Scale.
- Change from pre-treatment baseline in psychological well-being (e.g. overall mental well-being and discrete emotional problems such as anxiety, depression, somatization) to post treatment, and at quarterly follow-ups

- Change from pre-treatment baseline in health care use to post-treatment, and at quarterly follow-ups
- Gains in estimated quality adjusted life years (QALYs) from pre- to post-treatment
- Change from pre-treatment baseline in extraintestinal symptoms to post-treatment, and at quarterly follow-ups
- The percent of participants responding positively to treatment as measured by the adequate relief of pain and adequate relief of bowel symptoms
- The percent of participants who report adequate relief, improved symptoms, and clinically significant reduction of IBS symptoms by week four (rapid response)
- Safety as measured by the occurrence of adverse events

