The EQ-5D⁷¹ is a standardized, non disease-specific instrument for evaluating participants' preference-based valuations of health-related quality of life. There are two sections to the EuroQoI: the EQ-5D and the EQ thermometer. The EQ-5D assesses health across five domains: anxiety/depression (AD), mobility (M), pain/discomfort (PD), self-care (SC), and usual activities (UA). Each domain has one item and a three-point

categorical response scale; health 'today' is assessed. Weights based upon societal valuations of health states are used to calculate an index score of -0.59 to 1.00, where -0.59 is a state worse than death and 1.00 is maximum well-being. A score profile can be reported. The EQ thermometer is a single 20 cm vertical visual analogue scale with a range of 0 to 100, where 0 is the worst and 100 the best imaginable health. The EQ 5D is added to testing battery for the purpose of gauging economic impact of treatments (Aim 4) in terms of quality-adjusted life year (QALY)⁷³.

CDC HRQOL-4 ("Healthy Days") The core items of the CDC HRQOL-4 ^{9, 74} (also referred to as "Healthy Days") include four questions. Question 1 is a global selfperceived health item (from excellent to poor) regarded as a valid synthesis of individuals' appraisals about their past, present, and anticipated health problems; for secondary analyses, question 1's five ordinal levels were collapsed into two dichotomous levels: 1) excellent, very good, and good, or 2) fair and poor. Three "days" questions measure poor physical health (question 2), poor mental health (question 3), and activity limitation resulting from poor physical or mental health (question 4) in the past 30 days. The sum of the responses to the second and third questions yields an "overall unhealthy days" measure that estimates the overall number of recent days when physical or mental health was not good with the restriction that the total number of days does not exceed 30 days. For example, a person who reports four physically unhealthy days and two mentally unhealthy days is assigned a value of six unhealthy days; someone who reports 30 physically unhealthy days and 30 mentally unhealthy days is truncated at the maximum of 30 unhealthy days to maintain the same timeframe as that of its components.

Disease-Specific QOL

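### The QALY endpoint stops at week 12 although EQ-5D is collected to 12 months, so it would miss most of a lasting gain

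*Protocol*

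**What the plan says.** Section 3.4 of the protocol gives the QALY endpoint as "Gains in estimated quality adjusted life years (QALYs) from pre- to post-treatment". The bullet just before it reads "Change from pre-treatment baseline in health care use to post-treatment, and at quarterly follow-ups", and the quality-of-life bullet reads "Change from pre-treatment baseline in indices of health related quality of life to post treatment, and at quarterly follow-ups". Within this list, then, post-treatment and the quarterly visits are separate time points, and the QALY bullet names only the first. Section 2.1 dates that point: "Participants will undergo post-treatment evaluation two weeks after their assigned treatment ends (week 12").

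On data collection, the Appendix 7 schedules mark EQ-5D at baseline (Book 1) and at week 12 and months 3, 6, 9 and 12 (Book 3). Appendix 8 says that the instrument was included "for the purpose of gauging economic impact of treatments (Aim 4) in terms of quality-adjusted life year (QALY"), and sets no horizon. It also has the economic form completed at baseline, after the acute phase and at each quarterly visit.

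On duration, section 2 says "The acute treatment phase will last 10 weeks", with follow-up at week 12 and then "three, six, nine, and 12 months after the end of treatment". Aim 5 in section 3.2 hypothesises that both CBT arms keep their advantage over attention control through that period.

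**The concern.** A QALY is utility accumulated over time, so the horizon largely determines the result. A window that closes two weeks after therapy ends covers the period in which benefit is still building and little of the period in which a lasting benefit would accrue. The endpoint as worded therefore sets aside follow-up utility values that the trial collects for this purpose.

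The cost of delivering therapy falls within the 10-week acute phase. If a cost per QALY against attention control were built on this endpoint, the full delivery cost would be set against a small part of a durable benefit.

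**Working it through.** The protocol states no QALY figure, EQ-5D effect size or power for this endpoint, so there is nothing to reproduce. The check is the share of the total QALY gain that falls inside the stated window.

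**Inputs**
- Window as written: week 0 to week 12 (sections 3.4 and 2.1).
- Last visit: 10 weeks of treatment plus 12 months (52 weeks) = week 62 by the text of section 2. The Appendix 7 follow-up heading prints week 52 for month 12. Both are used.
- Utility gain over control at week 12: *u*. It is not in the documents, but it cancels in the share.
- Shape over time (assumed): linear rise to week 12, then the patterns below.

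**Formulas** (areas in *u*-weeks; divide by 52 for QALYs)
- Inside the window: 0.5 × 12 = 6.
- After week 12, maintained to week H: H − 12.
- After week 12, linear decay to zero at week T: 0.5 × (T − 12).
- Share captured = 6 / (6 + area after week 12).

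| Pattern after week 12 | Last visit week 62 | Last visit week 52 |
|---|---|---|
| Maintained (Aim 5) | 6/56 = 10.7% | 6/46 = 13.0% |
| Half lost linearly by last visit | 6/43.5 = 13.8% | 6/36 = 16.7% |
| All lost linearly by last visit | 6/31 = 19.4% | 6/26 = 23.1% |
| All lost by week 34 | 6/17 = 35.3% | 6/17 = 35.3% |
| All lost by week 22 | 6/11 = 54.5% | 6/11 = 54.5% |

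Under linear decay the share reaches one half when 0.5 × (T − 12) = 6, that is at T = 24.

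**Sensitivity to onset.** If the gain appears at once and is maintained, the share is 12/62 = 19.4% or 12/52 = 23.1%.

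**Illustration in QALYs.** For an assumed *u* of 0.05 with the gain maintained, the window gives 0.05 × 6/52 = 0.0058 QALY. The full horizon gives 0.05 × 56/52 = 0.0538 to week 62, or 0.05 × 46/52 = 0.0442 to week 52. For *u* from 0.03 to 0.10, the window gives 0.0035 to 0.0115, against 0.0323 to 0.1077 to week 62.

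**Cost per QALY against control, if built on this endpoint.** With intervention cost held fixed, the ratio is inflated by the reciprocal of the share: 56/6 = 9.3 times (week 62) or 46/6 = 7.7 times (week 52) if maintained, and 31/6 = 5.2 or 26/6 = 4.3 times if the gain decays to zero by the last visit.

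**The case against.** A reader might infer that the short horizon could overturn the Aim 4 conclusion. The documents do not support that. The cost-effectiveness text in section 7.4 refers to effectiveness only in terms of changes in IBS-related outcomes, and its example is cost per reduction in health care use. It neither names QALYs as the measure nor sets a week-12 horizon, and Appendix 8 sets none for EQ-5D. A 12-month QALY in Aim 4 is therefore not excluded. The documents give no incremental cost or willingness-to-pay figure from which a reversal could be shown.

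A reader might also infer that durability is ignored. It is not. Appendix 8 places EQ-5D among the quality-of-life questionnaires, and the quality-of-life endpoint runs to the quarterly visits. Aim 5 has its own growth-curve analysis. Only the time-integrated measure is cut short, and no data are lost.

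The direction of the distortion depends on the result. Section 7.4 allows that MC-CBT benefit may fade faster than S-CBT benefit, so for that comparison the direction is unknown. With fast decay the omitted share is modest.

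Appendix 8 also uses the term post-treatment more loosely, for several visits. That weakens certainty about intent, but the parallel wording within section 3.4 makes week 12 the natural reading.

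Finally, the area-under-curve method and the baseline adjustment are commonly left to an analysis plan, so their absence is not criticised here. What stands is the horizon that section 3.4 states, which nothing else in the protocol extends.

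**Conclusion.** The point holds as a matter of endpoint definition. The QALY endpoint ends at week 12, while the utility data meant for it run to 12 months after treatment. If the effect lasts as Aim 5 hypothesises and builds linearly to week 12, about 87% to 89% of the gain lies outside the window. With complete linear loss by the last visit it is 77% to 81%, and with loss by week 34 it is 65%. The omitted share falls below half only if the effect has gone by about week 22 (45.5% omitted). These shares do not depend on the size of the EQ-5D effect; they do depend on the assumed shape and duration.

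The effect on Aim 4 against attention control is conditional on this endpoint being used there. For MC-CBT against S-CBT no direction can be stated.

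**What to change.** Redefine the endpoint in section 3.4 as QALYs from baseline through the 12-month follow-up. Calculate them as the area under the EQ-5D utility curve over all scheduled assessments, adjusted for baseline utility, and over the same horizon as the costs. Keep the week-12 figure as a short-horizon sensitivity result.

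Reconcile the week 52 printed for month 12 in Appendix 7 with follow-up counted from the end of treatment (about week 62), because this sets the time base for the area.

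The change affects wording and analysis only and needs no new visit or instrument. Its cost is more missing EQ-5D values over the longer horizon.

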3.5 Pain Intensity Responder

- Decrease in weekly average amount of "worst abdominal pain in past 24 hours" score of
 > 30%
- Pain graded on a 11 point Numerical Rating Scale (NMRS) of 0-10 (where 0 = no pain, 10 = worst pain imaginable)

3.6 Stool Frequency Responder

- An increase of at least 1 complete spontaneous bowel movement (CSBM) per week from baseline
- For IBS-D, a participant is regarded as a weekly responder on the basis of pain intensity and stool consistency

3.7 Stool Consistency Responder

• Equal or less than type 5 in weekly average of the Bristol Stool Form Scale

4. STUDY POPULATION

4.1 Number of Sites and Participants

The sample will consist of 480 adult (18-70 inclusive) volunteers (240 participants x two sites) who meet Rome III diagnosis of IBS. The sites were chosen partly to yield a geographically and ethnically diverse sample that is broadly representative of individuals with IBS. The IBSOS infrastructure includes the Administrative Core (CC) at the University at Buffalo (Buffalo, New York). The AC is directed by Project PI [name]. Northwestern University Feinberg School of Medicine (Chicago, Illinois), the other clinical site, is led by SI [name], who serves as vice chair of the IBSOS. The AC at UB is responsible for oversight for both clinical sites. Each clinical site is responsible for the recruitment, retention, and safety of their participants and for the acquisition and integrity of the study data.

See Appendix 3: Study Organizations

4.2 Participant Eligibility

The eligibility criteria for IBSOS identify adult participants with moderate to severe IBS who are likely to adhere to the intervention, for whom the intervention is safe, and whose data can be interpreted clearly. The inclusion and exclusion criteria are primarily based on Drs. [name], [name] and [name]'s experience with NIDDK R01, "Cognitive Therapy for IBS: Process, Predication, and Outcome"; [name] pilot study, "Development of a limited contact CBT for IBS"; and guidelines for the conduct of clinical trials for therapies of functional GI disorders. The logic behind our eligibility criteria is to be as unrestrictive as possible while ensuring the safety of participants and maintaining the internal validity of the study.

See Appendix 4: Eligibility Criteria

4.3 Participant Recruitment

A key factor that determines the success of any clinical trial is recruitment of eligible participants of an adequate sample size. Low rates of recruitment have negative implications, such as longer duration of the clinical trial, which may lower staff and participant morale, a costlier clinical trial, since extra resources may need to be allocated to the recruitment effort, and reduced statistical power. Like all trials, the IBSOS requires the expeditious enrollment of a sufficient number of participants to ensure the statistical power and generalization of study results. This trial plans to recruit 480 participants over an approximately four-year treatment delivery period. Assuming a relatively conservative pre randomization dropout rate of 25%, each site will **need to phone telephone screen approximately 150 participants per year and enroll (consent) 75 in order to meet yearly recruitment quotas of 60 randomized participants at each site.**

Based on the PIs' (Drs. [name], [name]) success in meeting accrual goals in two NIH trials with similar eligibility criteria as the proposed trial, the lead investigators anticipate no difficulty meeting enrollment goals and have formally committed to meeting yearly accrual goals as scheduled prior to grant submission. The sooner IBSOS can achieve its enrollment goals, the faster data are collected, analyzed, and shared with the larger community to improve the management of IBS.

4.4 Recruitment and Retention Plan

Site investigators will formally present their formal recruitment plan at the initial four- to five-day training workshop before recruitment is initiated. The sites will review their plans continually throughout recruitment in order to determine its effectiveness and report progress to the Steering Committee regarding failed screens, the productivity of recruitment strategies, and barriers to recruitment. Data shared with the SC will include number of inquiries, telephone screens, recruitment methods (self-referral, health care provider, broadcast media, etc.), and the rate of screen-to-evaluation turnover. If a center is not achieving its recruitment goals in a timely fashion, the recruitment plan may need to be modified.

It is expected that the research team at each site and across the sites will form a dynamic system of support for problem solving and developing of IBSOS-specific recruitment techniques that expeditiously meet the accrual goals of the trial.

Each clinical center will develop a formal site-specific recruitment plan for meeting the recruitment goals and requirements of IBSOS. It is expected that the plan will address any unique features of catchment area characteristics, media market outlets, anticipated barriers (participant-, investigator-, and protocol-related) and strategies for working around them, and access to IBS participants. When composing such a plan, attention should be paid to issues regarding research ethics and strategies to enhance diversity in the study population.

5. ASSIGNMENT TO TREATMENT GROUPS

5.1 Randomization

Participants in the IBSOS will be randomly assigned to one of three treatments. Random assignment is important to ensure that the different experimental treatments will be given to comparable groups of participants. Treatment assignments will be generated using an existing web-based participant registration and randomization system at Frontier Science. This system uses protocol-specific specifications files to present questions to the sites to evaluate a participant for eligibility. Only participants who meet all the eligibility requirements can be randomized to the study. The participant enrollment system also collects basic demographic information at the time of enrollment. The Protocol Data Manager at Frontier Science will work with the Principal Investigator and Project Statisticians to develop these files based on the eligibility criteria of the protocol. Treatment allocation assignments are stratified by clinic site. This will ensure initial comparability between groups of eligible participants, for whom treatments are compared, thus eliminating the impact of individual and site difference variables on outcome.

5.2 Blinding

In most RCTs, participants and the treating physician are "blind" or "masked" to the treatment and do not know if the participant is receiving drug or placebo. The methodological criterion of blinding participants to assigned treatments is inapplicable to psychological interventions ¹. To the extent that blinding seeks to control differential expectations and consequent demand characteristics they may generate, then we will adopt the established, surrogate practice of having participants rate credibility of the treatment to which they were assigned and their expectancy of improvement using the Treatment Expectancy Scale ² at the conclusion of Session 1.

See Appendix 5: Adverse Event Reporting

See Appendix 6: Interruption or Discontinuation of Therapy

6. DESCRIPTION OF THERAPY

The IBSOS features two specific types of psychological treatment, either Education Supportive Counseling (Attention Control Condition) or Cognitive Behavior Therapy (CBT). Cognitive Behavior Therapy will be delivered in two "dosages": a home-based, self-administered version (four sessions) or a clinic-based, therapist delivered version (10 sessions). In this respect, the trial features three discrete treatment conditions:

- Ten-session, therapist-administered CBT
- Four-session, participant-administered CBT
- Four-session Attention Control Condition

The Attention Control Condition represents a credible attention-placebo condition that provides adequate control for the non-specific factors (e.g. attention from university-based medical staff and faculty) that foster improvement in participants treated with CBT. Thus, the trial will feature three treatment arms. All treatments will be manualized and conducted on an individual, outpatient basis by a highly trained therapist.

Complete explanations of these therapies can be found in the Treatment Manuals. The following section provides a brief summary of the nature, structure, and format of featured treatments:

6.1 Standard CBT (S-CBT)

S-CBT is a skills-based training program ³ that involves 10 weekly, one-hour individual sessions. Treatment is structured around six overlapping phases:

- 1. Information and education regarding stress and its relationship to IBS
- 2. Self-monitoring of stressful situations associated with IBS episodes
- 3. Muscle relaxation exercises both to increase physiological self regulation and to cultivate a sense of mastery or self control over symptoms

- 4. Learning to identify, reevaluate, and change negatively skewed thoughts associated with IBS
- 5. Changing underlying schemas or "core" beliefs (e.g. perfectionism)
- 6. Formal training in problem solving to strengthen the ability to cope more effectively with realistic stressors associated with IBS weekly home exercises are assigned to facilitate skills acquisition.

6.2 Minimal-Contact CBT (MC-CBT)

MC-CBT covers the same range of procedures featured in S-CBT but relies extensively on self-study materials to facilitate skills building. Additionally, whereas the S-CBT condition involves 10 one-hour clinic visits, MC-CBT meets for only four, one-hour clinic visits over a 10-week period.

- 1. At the first MC-CBT session, treatment is explained, self-study materials are provided and muscle relaxation and self-monitoring are introduced.
- 2. The second treatment session introduces cognitive coping techniques (e.g. decatastrophizing through prediction testing).
- 3. At the third session, participants learn problem-solving techniques and more advanced cognitive coping skills (e.g. modifying core beliefs such as perfectionism).
- 4. The fourth session introduces relapse prevention skills.

In the MC-CBT condition, two 10-minute phone contacts are scheduled at weeks 3 and 7 to troubleshoot around any problems encountered between clinic visits.

